### 13.2 Annual Progress Report (APR)

#### Non-UK sites

If required, according to local guidelines, the APR will be written and submitted to the Ethics committee by the Lead Research team of each country. A copy will be provided to the sponsor.

## 14.0 Statistical and data analysis

#### 14.1 Sample size calculation

The primary analysis of the trial is the comparison between Group 1 and Group 3 (see figure in Section 2.6), i.e. the patients classified as biomarker positive treated with Abatacept + Methotrexate (MTX) (Group 1) vs. the patients classified as biomarker negative treated with Abatacept + Methotrexate (MTX) (Group 3). Since patients will be randomised 1:1 to either Abatacept + MTX or Placebo + MTX and the median value observed in the PEAC study as a cut-off to classify the biomarker status, we expect the comparison groups to be roughly equal. That would allow to ascribe the differences in response we will observe to the different biomarker profiles of the two groups, hence demonstrating if the presence of a biomarker will enhance the response to the any of the drugs included in the trial.

The power calculation is done for this comparison, based on the following assumptions:

50% patients will be classified as biomarker positive and 50% as biomarker negative
 Using change in CDAI score from baseline (delta CDAI) as the primary outcome, a difference in delta CDAI between the two comparison groups of 10, with a Standard Deviation of 14.34. These are the values that were observed when analysing the difference in delta CDAI between biomarker positive and biomarker negative patients treated with MTX in the PEAC study. Although PEAC patients were not treated with Abatacept, this comparison is expected to be even more in favour of the biomarker positive group using Abatacept together with MTX. Thus, basing the power calculation on the PEAC observed difference is a conservative assumption.

With these assumptions, 88 patients would be needed to detect a significant difference of 10 in delta CDAI with 90% power (66 patients for 80% power). Since this would only be for Group 1 and Group 3 (44 patients each), a total of 176 patients would be sufficient for 90% power in the whole trial (132 for 80% power) which includes all four groups as per Figure 1 Section 2.6. If we assume a 5% dropout rate and also account for an expected 5% of patients that have insufficient RNA for the Nano-string analysis (based on results from the STRAP trial), 196 patients in the whole trial would be sufficient to detect a significant difference (Group 1 vs Group 3) of 10 in delta CDAI with 90% power (147 patients for 80% power).

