#### 1.1 Background

A previous observational study performed at the Centre of Experimental Medicine and Rheumatology called the 'Pathobiology of Early Arthritis Cohort' (PEAC) demonstrated the presence of three distinct pathology groups in patients with RA; namely the a) lympho-myeloid b) diffuse-myeloid and c) pauci-immune pathotypes. These pathotypes are characterised by the a) presence of B cells and myeloid cells b) cells of the myeloid lineage but poor in B cells and c) scarce immune cells with a predominance of stromal cells in the synovium respectively. In addition to histological analysis of the synovium, molecular analysis of the synovium was also undertaken by RNA sequencing. The lympho-myeloid phenotype was found to be associated with the highest level of erythrocyte sedimentation rate (ESR), C- reactive protein (CRP), anti-citrullinated protein antibody (ACPA) titre and DAS-28 ESR scores as well as greater erosive disease and a higher 'inflammatory signal on ultrasound. The pauci-immune pathotype on the other hand was associated with the lowest levels of ESR and CRP, rheumatoid factor (RF) and ACPA positivity and US scores despite high DAS-28 ESR scores. At a molecular level, gene expression signatures were found to correlate with response to csDMARD therapy. For example, the myeloid and lymphoid scores were associated with greater response to csDMARDs as measured by larger decreases in DAS28-ESR posttreatment.

Abatacept is indicated for moderate to severe active rheumatoid arthritis (RA) in adult patients who responded inadequately to previous therapy with one or more disease-modifying antirheumatic drugs (DMARDs) including methotrexate (MTX) or a tumour necrosis factor (TNF)alpha inhibitor. In this trial DMARD naïve RA patients with <12 months symptom duration will receive MTX + placebo or MTX + abatacept, so abatacept is prescribed "off-label" for patients at this stage of RA disease. Abatacept has been used in a number of early intervention trials and safety and efficacy as an early RA intervention has been demonstrated in the following trials: NORD-STAR^4, AGREE and AVERT. For example, in the NORD-STAR trial, compared with active conventional therapy, CDAI remission rates were significantly higher for abatacept. Additionally, in the trial, the proportion of SAEs was lowest in the abatacept group when compared to certolizumab, tocilizumab and active conventional therapy.

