# 2.1 Primary objective(s)

The primary objective of this trial is to determine whether synovial molecular profiles (=drug target signatures) can inform treatment response to abatacept in early RA.

To achieve this objective, we will compare the change in Clinical Disease Activity Index (CDAI) score at 16 weeks between the biomarker positive and the biomarker negative patients within the abatacept group (i.e. Group 1 vs Group 3) Fig.1 Trial Design.

We hypothesise that patients with high synovial immunological infiltrate (lymphoid pathotype) will respond better to abatacept therapy.

[figure not shown]
[figure not shown]

Fig. 1: Trial Design

[figure not shown]

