# 2.2 Secondary objective(s)

We aim to assess patients treated according to their biomarker: comparing the biomarkerpositive patients (as Groups 1 minus 2) vs the biomarker-negative patients (as Groups 3 minus 4).

Barts

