#### 14.7 Primary endpoint analysis

The primary analysis is within the abatacept arm. It will assess the difference in the change in Clinical Disease Activity Index (CDAI) score at 16 weeks between the biomarker positive and the biomarker negative patients (i.e. Group 1 vs Group 3). This analysis will be on an ITT basis according to original randomisation allocation. The primary outcome will be analysed by analysis of covariance (ANCOVA) with treatment as a factor and baseline value as continuous covariate. If assumptions for ANCOVA are not met, non-parametric ANCOVA will be used. The treatment effect will be reported as least squares mean with 95% confidence intervals.

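### Group 1 vs Group 3 shows association with outcome on abatacept plus methotrexate; it cannot demonstrate that the biomarker enhances response to abatacept, as section 14.1 says

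*Protocol*

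**What the plan says.** The primary objective (protocol 2.1) is whether synovial molecular profiles "can inform treatment response to abatacept in early RA". Section 14.1 fixes the test: "The primary analysis of the trial is the comparison between Group 1 and Group 3", that is, biomarker-positive against biomarker-negative patients who all receive abatacept plus methotrexate. Section 14.7 confirms it: "The primary analysis is within the abatacept arm". Oral methotrexate is given in all four groups (7.5.6).

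Section 14.1 then says that differences between the two groups can be ascribed to their biomarker profiles, "hence demonstrating if the presence of a biomarker will enhance the response to the any of the drugs included in the trial".

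The sample size uses a difference of 10 in delta CDAI with SD 14.34. On their origin in the earlier PEAC cohort the protocol says: "These are the values that were observed when analysing the difference in delta CDAI between biomarker positive and biomarker negative patients treated with MTX". It adds that those patients had no abatacept, expects abatacept to widen the gap, and on that ground calls the assumption conservative.

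The placebo groups enter only through the secondary objective (2.2), "comparing the biomarkerpositive patients (as Groups 1 minus 2) vs the biomarker-negative patients (as Groups 3 minus 4", which 14.8 applies to the primary and secondary endpoints. No size or power is given for it.

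**The concern.** A comparison of two biomarker strata on one treatment shows whether the strata have different outcomes on that treatment. The difference can arise in three ways: the biomarker marks a better course whatever is given, it marks better response to methotrexate, or it marks better response to abatacept. Group 1 vs Group 3 adds the three together. Only the placebo groups, which receive the same methotrexate background, can isolate the third.

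This matters here because the protocol's own planning value is a difference seen on methotrexate without abatacept. A significant primary result may therefore be likely even if the biomarker has no bearing on abatacept. Read through the inference in 14.1, that result would be reported as evidence for choosing abatacept by biopsy.

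**Working it through.** **Inputs.** Difference 10, SD 14.34, 44 per group for 90% power and 33 for 80%, inflation of 5% + 5% (all section 14.1). Significance level and sidedness are not stated there; two-sided 0.05 is assumed. It agrees with the 95% intervals in 14.7 and reproduces the plan's figures, whereas one-sided 0.05 would give 36 and 26 per group.

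**1. The plan's own figure.** n per group = 2 × [SD × (z₀.₉₇₅ + z_power) / difference]².
- 90%: 2 × (14.34 × 3.2415 / 10)² = 43.2, so 44 per group, 88 in Groups 1 and 3, 176 in four groups; 176 / 0.90 = 195.6, so 196.
- 80%: 2 × (14.34 × 2.8016 / 10)² = 32.3, so 33 per group, 66, 132; 132 / 0.90 = 146.7, so 147.

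All stated figures reproduce.

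**2. Chance of a significant primary result with zero interaction.** Let the methotrexate-only difference D be present in both arms and let abatacept add the same amount to both strata. The expected Group 1 vs Group 3 difference is then D. Its SE = 14.34 × √(2/44) = 3.06. At D = 10 the standardised difference is 10 / 3.06 = 3.27, giving 90.5% by the normal approximation and 89.9% by the noncentral t. This is the plan's own power calculation, read under a different truth. A simulation of 50,000 four-group trials with zero interaction gave 89.9% for Group 1 vs Group 3 and 5.1% for the interaction test.

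Range over the carried-over difference (44 per group, noncentral t):
- 10 points: 90%
- 8 points: 73%
- 6 points: 49%
- 5 points: 37%
- 4 points: 25%
- 2 points: 10%

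**3. Effect of baseline adjustment.** These figures are unadjusted, while the planned model is ANCOVA on baseline CDAI. If the difference is unchanged by adjustment, the residual SD is 14.34 × √(1 − ρ²), and a baseline correlation ρ of 0.3 to 0.5 (assumed) raises the 90% to 92–96%. If biomarker-positive patients start with higher CDAI, adjustment could instead shrink the difference and lower the figure. The protocol does not settle which.

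**4. Precision of (G1-G2)-(G3-G4).** SE = 14.34 × √(4/44) = 4.32.
- Interaction of 10 points: 10 / 4.32 = 2.31, power about 63% (noncentral t; 64% by the normal approximation).
- Interaction of 5 points: power about 21%.
- 80% power needs 4.32 × 2.80 = 12.1 points; 90% needs 4.32 × 3.24 = 14.0 points.
- To detect 10 points: 65 per group (260 evaluable) for 80% and 87 per group (348) for 90%.

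**The case against.** The strongest reply is that the trial already collects what is needed: all four groups exist, and the difference of differences is a stated secondary objective. That stands. The defect lies in the inference attached to the primary contrast, and nothing in the text makes that inference depend on the secondary one.

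Four stronger readings are tempting, and the protocol does not support them.
- *The primary test will be significant 90% of the time whatever abatacept does.* That needs the PEAC estimate to be the true methotrexate-only difference and to carry over in full. It is one observed estimate, so the range in step 2 belongs with the figure.
- *Calling the assumption conservative is wrong.* For the power of Group 1 vs Group 3 it is reasonable if abatacept widens the gap, as the sponsor expects. It says nothing about the abatacept-specific question, but 14.1 does not attach it to that question.
- *Section 1.1 already shows that this biomarker tracks methotrexate response.* Its statement that "the myeloid and lymphoid scores were associated with greater response to csDMARDs" concerns those scores and DAS28-ESR. The trial classifier is CD80/CD86 status (2.6, 7.3), and only the PEAC comparison in 14.1 bears on it directly.
- *The interaction must replace the primary test.* That is a trade-off: at the planned size the interaction test has about 63% power for 10 points. Leaving a secondary contrast unpowered is ordinary practice, and the protocol gives no expected interaction size, so the 10 and 5 points used here are illustrative.

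It is also fair to say that biomarker status is not randomised in the interaction contrast either. A correlate of the biomarker could explain effect modification, although prognosis common to both arms does cancel.

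**Conclusion.** The sentence in 14.1 is wrong as written. Group 1 vs Group 3 estimates the association of the biomarker with outcome on abatacept plus methotrexate and does not identify an abatacept-specific effect. That conclusion follows from the design and needs no numerical assumption.

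The size of the problem does need assumptions: full additive carry-over of the PEAC difference, 44 evaluable per group, SD 14.34, two-sided 0.05 and no baseline adjustment. Under these a significant primary result has about 90% probability with no interaction at all. With a carried-over difference of 4 to 8 points it has 25% to 73%, still well above 5%. The planned difference of differences answers the question, with less precision than the 90% headline power suggests.

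**What to change.** 1. In 14.1, replace the sentence on demonstrating enhanced drug response with a statement that Group 1 vs Group 3 estimates the association of the biomarker with response on abatacept plus methotrexate. The word conservative may stay if it is limited to the power of that contrast.
2. In 2.1 and 14.7, state that no conclusion that the biomarker predicts benefit from abatacept will be drawn unless (G1-G2)-(G3-G4) supports it. Estimate that contrast from one four-group ANCOVA with biomarker, treatment, biomarker × treatment and baseline CDAI, and report it with a 95% confidence interval.
3. In 14.1, state its precision at 44 per group: SE about 4.3, power about 63% for 10 points and 21% for 5, with about 12 points needed for 80% power and about 14 for 90%.

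Group 1 vs Group 3 may remain the primary test. The cost is wording and one model on data already being collected, with no extra patients or visits. The downside is that the stated power for the abatacept-specific claim will be below 90%. Sizing the trial for a 10-point interaction at 90% power would take 348 evaluable patients, or 348 / 0.90 = 387 with the protocol's inflation; that is a separate decision and is not required by this point.

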#### 14.2 Planned recruitment rate

This study will include at least 10 recruiting centres and recruitment rates at each centre will be reviewed at regular 3TR RA working group meetings. If the recruitment rate is slower than expected, additional centres and PIC sites may be set up in order to meet the recruitment target.

#### 14.3. End of trial (EOT)

The end of the study will be triggered 6 months after the last patient completes their final study visit (Last Patient Last Visit LPLV).

These additional 6 months will allow time for sample processing and image analysis. The end of trial declaration will be submitted within 90 days of the end of trial definition, and this will mark the end of trial data and sample collection, sample and image analysis.

The CI is delegated the responsibility of submitting the EOT notification to REC and MHRA once reviewed by the sponsor. The EOT notification must be received by the REC and MHRA within 90 days of the end of the study. If the study is ended prematurely, the Chief Investigator will notify the Sponsor, REC, and MHRA within 15 days, including the reasons for the premature termination.

For non-UK sites, the reporting of the end of trial to the ethics committee and Competent authority will be delegated to a lead research team in that country. The sponsor (JRMO) must be sent a copy of the correspondence with regards to this matter.

The clinical study report will be submitted within 12 months of the end of trial notification.

#### 14.4 Statistical Analysis

The statistical analysis of the trial will be described in detail in the Statistical Analysis Plan (SAP). This will be finalised prior to the analysis of the data. In brief, the primary outcome, which is a continuous outcome, will be analysed by analysis of covariance (ANCOVA) with treatment as a factor and baseline value as continuous covariate. If assumptions for ANCOVA are not met, non-parametric ANCOVA will be used. Changes from baseline within groups will be analysed with a paired Wilcoxon test. Secondary binary endpoints will be analysed using a  $\chi^2$  test unless any element within the contingency table has fewer than 5 individuals in which case a Fisher's exact test will be used.

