#### 2.3.2 Secondary endpoint(s)

- 1. Percentage of patients with DAS28<3.2 (LDA) at 16 weeks.
- 2. Percentage of patients deemed responders using American College of Rheumatology 50 (ACR50) measure at 16 weeks.
- 3. Percentage of patients with CDAI remission at 16 weeks.
- 4. Change in HAQ-DI at 16 weeks from baseline.
- 5. Change in SF-36 at 16 weeks from baseline

Secondary endpoints will be reported descriptively within each treatment group.

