#### 14.8 Secondary endpoint analysis

The primary analysis will be repeated using the secondary endpoints.

The primary and secondary endpoints will also be used to perform analyses comparing the difference in response between the abatacept and placebo groups with the biomarker positive group against the difference in response between the abatacept and placebo groups with the biomarker negative group.

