#### 14.10 Subgroup analyses

Response in individual treatment groups, both overall and by arm, will be presented descriptively.

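### Section 14.4 tests change from baseline inside each group without a control, 2.3.2 contradicts 14.4 and 14.8 on the secondary endpoints, and no abatacept-minus-placebo estimate is stated by stratum or overall

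*Protocol*

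**What the plan says.** Patients are stratified by biomarker and randomised 1:1 to abatacept or placebo, both with methotrexate (2.6, 7.3). This gives Group 1 (positive, abatacept), Group 2 (positive, placebo), Group 3 (negative, abatacept) and Group 4 (negative, placebo).

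- **14.4, within-group tests:** "Changes from baseline within groups will be analysed with a paired Wilcoxon test". No endpoint, purpose or caveat is attached.
- **14.4, secondary binary endpoints:** a chi-squared test, unless a cell is small, "in which case a Fisher's exact test will be used".
- **14.7:** "The primary analysis is within the abatacept arm", a baseline-adjusted ANCOVA of Group 1 against Group 3.
- **14.8:** "The primary analysis will be repeated using the secondary endpoints". It adds an analysis "comparing the difference in response between the abatacept and placebo groups with the biomarker positive group" against the same difference in the biomarker-negative group. This matches the secondary objective in 2.2.
- **2.3.2:** "Secondary endpoints will be reported descriptively within each treatment group".
- **14.10, under subgroup analyses:** "Response in individual treatment groups, both overall and by arm, will be presented descriptively".

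**The concern.** A before-and-after test asks whether a group changed, not whether abatacept changed it. Here the groups are very likely to change. All patients are DMARD-naive and start methotrexate (6.1, 7.5.6), corticosteroids are allowed at the clinician's discretion (11.15.3), and entry requires DAS28 above 3.2 (6.1), which invites regression to the mean. Each of these counts towards rejection in every group. If one group is significant and another is not, a reader may infer a difference that was never tested.

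Two further matters sit beside this. The placebo arm enters the stated analyses only as part of a difference of differences, so the simple randomised effects (1 v 2, 3 v 4, overall) have no stated result. And 2.3.2 gives the secondary endpoints a different treatment from 14.4 and 14.8, so an analysis plan that followed one passage would depart from another.

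**Working it through.** **Inputs.** From 14.1: SD of change in CDAI 14.34, 44 per group, difference of 10 between biomarker-positive and biomarker-negative patients. Assumed: two-sided 5% level (14.1 states none), normally distributed changes, and a shared mean CDAI fall of 5, 7.5 or 10 in two arms with no abatacept effect. The protocol gives no mean fall, hence the range.

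**The plan's own figure.** n per group = 2 × SD² × (1.960 + 1.282)² / 10² = 2 × 205.6 × 10.51 / 100 = 43.2, so 44. Two groups make 88 and four make 176; 176 / 0.90 = 195.6, so 196. The stated figures reproduce.

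**Within-group test with no abatacept effect.** The standard error of a group's mean change is 14.34 / √44 = 2.16. The normal approximation to the rejection rate is Φ(fall / 2.16 − 1.96). The simulated Wilcoxon columns use 2,000 pairs of groups.

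| Shared fall | Normal approximation | Wilcoxon, simulated | Exactly one of two identical arms significant |
|---|---|---|---|
| 5 | 64% | 62% | 47% |
| 7.5 | 93% | 91% | 17% |
| 10 | 99.6% | 99.4% | 1% |

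The last column agrees with 2p(1 − p) for independent arms: 2 × 0.616 × 0.384 = 0.473; 2 × 0.906 × 0.094 = 0.170; 2 × 0.994 × 0.006 = 0.012. In a separate simulation of 4,000 trials, a between-arm t-test on such data was significant in 4% to 5% of trials at falls of 5 and 10, as it should be.

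**What the planned contrast can and cannot show.** A common methotrexate response cancels within (1 − 2) and within (3 − 4). But the contrast is one number. A value of 10 arises from a benefit of 10 in biomarker-positive patients and 0 in biomarker-negative patients. It arises equally from 0 in the positive and a 10-point disadvantage in the negative. Only the two component differences separate these cases.

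**Precision of the estimates not stated.** Approximate 95% half-widths, before any gain from baseline adjustment:
- per stratum, 44 v 44: 1.96 × 14.34 × √(2/44) = 6.0 points
- overall, 88 v 88: 1.96 × 14.34 × √(2/88) = 4.2 points
- planned contrast: 1.96 × 14.34 × √(4/44) = 8.5 points

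**Secondary endpoints, side by side.** Section 2.3.2 has description within group. Section 14.4 tests the binary ones, 14.8 repeats a between-group analysis on all of them, and the table in 2.5 gives their purpose as checking the robustness of the primary analysis, which is a between-group comparison. For the change endpoints (HAQ-DI, SF-36), the only test in 14.4 whose wording reaches them is the within-group Wilcoxon; the between-group version comes only from 14.8.

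**The case against.** The strongest reply is that the randomised control is in the plan. Sections 2.2 and 14.8 form abatacept minus placebo in each stratum and contrast the two, for primary and secondary endpoints. That is the correct guard against reading a difference into one significant and one non-significant group. A reader might infer that abatacept is never compared with placebo; the documents do not support that. Nor does 2.3.2 say that the secondary endpoints are described only.

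Second, the Wilcoxon sentence is one line in a summary that defers detail to the SAP, and no passage uses its result to claim efficacy. That stands: the risk is misreading, not a planned false claim. But the test is stated, so this is not merely detail left for later.

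Third, the trial asks whether the biomarker informs response, and supportive contrasts are often left to a SAP. Their absence alone would not be a finding. They belong here because they should replace a stated test that cannot answer the question, and because they are already components of the 14.8 contrast.

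Fourth, the 47% is close to the 50% maximum and fades quickly. The 10-point gap in 14.1 also implies a fall of at least 10 in biomarker-positive patients on methotrexate, unless the negative ones worsened; discordance in that stratum would then be about 1%. This is fair. At such falls, though, both the abatacept and the placebo groups are almost always significant, so the test is uninformative either way.

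Finally, it is tempting to quote power for abatacept against placebo at the 10 points in 14.1. That figure is a biomarker-positive against biomarker-negative difference under methotrexate, so it does not serve as a treatment effect. Only precision is given above.

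**Conclusion.** The point holds in a limited form, and is worth correcting although it leaves the primary analysis untouched.

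- The within-group Wilcoxon tests cannot isolate abatacept. With no abatacept effect they are significant in about 62% of cases at a shared fall of 5 and over 99% at 10. This rests on the protocol's SD and group size, normal changes, a two-sided 5% level and assumed falls.
- Placebo is used through the (1 − 2) against (3 − 4) contrast, but no abatacept-minus-placebo estimate per stratum or overall is stated. The contrast alone does not show whether biomarker-positive patients benefit.
- Section 2.3.2 contradicts 14.4 and 14.8 on the secondary endpoints. This part needs no assumption.

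**What to change.** 1. In 14.4, replace the Wilcoxon sentence with a statement that within-group changes are shown as means or medians with 95% confidence intervals, without tests.
2. In 14.4 or 14.8, add that abatacept minus placebo at week 16 is estimated by baseline-adjusted ANCOVA with 95% confidence intervals, within each biomarker stratum (Group 1 v 2, Group 3 v 4) and overall adjusted for stratum. Report these beside the (1 − 2) against (3 − 4) contrast and label them supportive.
3. Reword 2.3.2 so that the secondary endpoints follow the between-group analyses of 14.4 and 14.8, with within-group description as an addition.

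The cost is a few sentences and a few more model outputs, with no new data. The downside is three more contrasts on the primary endpoint, which is why they should be marked supportive and not confirmatory.
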